**Table 1. Measures and Administration**

| Measure                                                  | Domain                         | Baseline | During Intervention (Biweekly) | Follow-up Survey |
|----------------------------------------------------------|--------------------------------|----------|--------------------------------|------------------|
| Beck Scale for Suicidal Ideation (BSS)                   | Suicidal ideation              | X        | X                              | X                |
| Client Satisfaction Questionnaire (CSQ)                  | Satisfaction with intervention |          |                                | X                |
| Client Services Receipt Inventory-EU-Revised (CSRI-EU-R) | Health care utilization        | X        | X                              | X                |
| Columbia-Suicide Severity Rating Scale (C-SSRS) Screener | Suicidal ideation and behavior | X        | X                              | X                |
| MSRC Common Data Elements                                |                                |          |                                | X                |
| MSRC Standard Demographic Form                           | Demographics                   | X        |                                | X                |
| Outcome Questionnaire (OQ-45)                            | Psychological Distress         | X        | X                              | X                |
| Patient Health Questionnaire-9 (PHQ-9)                   | Depression                     | X        | X                              | X                |
| Posttraumatic Stress Disorder Checklist 5 (PCL-5)        | PTSD                           | X        | X                              | X                |
| Rand 36-Item Health Survey                               | Quality of life                | X        | X                              | X                |
| Self-Help Mobile Application Utilization Survey          | Use of readily available Apps  | X*       | X**                            | X*               |
| COVID-19 Questionnaire                                   |                                | X        | X                              | X                |

\*All study participants; \*\*Those allocated to the Active Control arm only

**Figure 2.**  
**Participant View**

*Random Allocation and Concealment.* Randomization to the Experimental or Active Control arms will be stratified by gender, force, and smartphone model. The block randomization schemes, using random block sizes of 2, 4, and 6, will be produced by [name] using Statistical Analysis System (SAS) PROC PLAN with a specified seed, prior to any recruitment. To ensure concealed allocation, participants will be designated by an identification number.

*Treatment Arms.* Experimental. Those allocated to Experimental arm will have access to the Cogito Companion for a three-month period post-

consent. Passive data collection will also occur during this period. As a secure, privacy-compliant mobile app, the Cogito Companion facilitates the non-invasive collection, transfer, integration, analysis, and reporting of objective behavioral indicators (Figure 2). The Cogito mobile sensing platform passively gathers behavioral information through an individual's normal smartphone usage. Measurements of location, call, and text patterns are recorded. These raw

**Figure 3. Clinician Dashboard**

measurements, which number in the tens of thousands per week, are fed into Cogito's algorithms to compute validated behavioral indicators. These indicators are presented as model scores in the Clinician Dashboard, which will be used to facilitate monitoring of behavioral changes (Figure 3). Further information regarding this process will be provided below and in Human Subjects Recruitment and Safety Procedures. Participants may also monitor their own behavioral changes overtime (Figure 3). Individual users will also be prompted to record an "audio diary" using the mobile app via their smartphone. An analysis of vocal qualities, rather than content, will produce a model score, which is provided to users and the research team. Participants will also be able to subjectively rate their mood at the time of the recording. Reminders to complete these "audio diaries" will occur biweekly, on an alternating schedule with the biweekly surveys. Nonetheless, participants will be able to leave as many "audio diaries" as they would like during the three-month period.

**Clinical Research Staff Outreach – Cogito Group.** Clinically-trained research team members will monitor the Clinician Dashboard each business day one time per day (excluding federal holidays and weekends). Clinical monitoring may include the review of responses for the following: the PHQ-9, BSS, C-SSRS Screener, and individual model scores derived by Cogito app algorithms. Lack of data may also prompt a clinical outreach. Further information regarding risk identification and clinical monitoring will also be provided below.

**PHQ-9 Monitoring.** Clinical team members will review PHQ-9, item 9 "Thoughts that you would be better off dead or of hurting yourself in some way." A response of 2 (more than half the days) or 3 (nearly every day) will prompt a clinical outreach call to the participant. A response of 1 (several days) will be considered for a clinical outreach call in conjunction with other Dashboard data and/or surveys.

**BSS Monitoring.** Clinical team members will review the BSS screening items (items 1-5). Any response of "2" on items 1- 4, will prompt a clinical outreach call.

**C-SSRS Screener Monitoring.** Clinical team members will review responses to the C-SSRS and conduct outreach based upon recent and/or current suicidal ideation and/or suicidal or self-harm behaviors. Specifically, we will outreach if the participant positively endorses thinking about how they may kill themselves, have had thoughts of killing themselves with intention of acting on these thoughts, and/or if they've started to work out details of how to kill themselves.

Using the same clinical thresholds described above, the Cogito app will send an automatic notification to the participant regarding their scores, as well as resources (e.g., Military and Veterans Crisis Line, Military OneSource, Military Health System provider contact information [individualized data entered by participant or study team]).

**Cogito Model Score Monitoring.** Model scores are presented both in number and color format (Figure 4). Red indicates scores 39 or below, yellow indicates scores between 40 and 79, and green indicates scores between 80 and 100. The higher the score, the "healthier" the individual's behaviors. Any drastic daily change in score (+/- change of 20) and/or two scores less than 20 may prompt a clinical outreach call.

**Active Control.** Participants randomized to the Active Control group will download MyCAP and have access to resources housed within this app for a three-month period post-consent. Participants will be provided information regarding the mHealth Tool apps, and provided basic information on how to download the apps. As noted above, participants will be provided biweekly surveys as listed in Table 1. Participants will get one notification when surveys are available. If surveys are not completed, participants may be sent a reminder to complete the surveys via MyCAP automatic reminder or the in-app messaging feature.

**Clinical Research Staff Outreach – Active Control.** Clinically-trained research team members will monitor the MyCAP dashboard each business day one time per day (excluding federal holidays and weekends); however, outreach will solely be based on survey data or lack thereof.

Similar to the Cogito group, the Active Control group will receive the PHQ-9, BSS, and C-SSRS Screener surveys biweekly. If participants' responses on the PHQ-9, BSS and/or the C-SSRS Screener meet the clinical threshold described above, they will receive an outreach call, as well as automatic notification from MyCAP with resources (e.g., Military and Veterans Crisis Line, Military OneSource, and Military Health System provider contact information [individualized data entered by participant or study team]). Lack of responses to surveys may also prompt clinical outreach. Further information regarding risk identification and clinical monitoring will be provided below.

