## IV. Research Methods

### A. Outcome Measure(s)

Aim 1. Outcome Questionnaire (OQ-45). The OQ-45 is a psychometrically sounds 45-item measure designed to evaluate key areas of mental health functioning, including symptom distress. It is a widely-accepted tool for identifying, tracking, and measuring behavioral health treatment outcomes.

Client Services Receipt Inventory-EU-Revised (CSRI-EU-R). This is a measure which queries regarding use of inpatient hospital, outpatient hospital, community based-day services, as well as primary and community care contacts. In addition to validating care documented in electronic medical records, it will be used to identify care received outside of the MHS. In a recent systematic review of self-report measures, use of this tool was noted as being a valid method for data collection on healthcare utilization.

Patient Health Questionnaire-9 (PHQ-9)\*. This is a frequently used and psychometrically sound self-report measure of depression.

Posttraumatic Stress Disorder Checklist 5 (PCL-5)\*. The PCL-5 is a self-report measure used to evaluate post traumatic symptom severity. Criteria is based on Diagnostic and Statistical Manual of Mental Disorders-5 criteria. Items are rated on a 5-point Likert scale.

Beck Scale for Suicidal Ideation (BSS)\* is the self-report version of the Beck Scale for Suicide Ideation. Concurrent validity (comparing patient and psychiatrist ratings) was reported as .90 ( $p < .001$ ) and internal reliability was similarly high ( $\alpha = .93$ )

Rand 36-Item Health Survey is a 36-item psychometrically sound quality of life outcome-measure that yields perceived physical and mental health functioning summary scores.

The Columbia-Suicide Severity Rating Scale (C-SSRS) Screener is a screening measure, administered by a clinician or electronically, that assesses for suicidal ideation and attempt behavior based on established definitions. The C-SSRS screener assesses intensity of suicidal ideation, specifically asking about frequency, duration, intrusiveness, controllability, and deterrents, as well as suicide-related behavior, such as actual attempts and aborted attempts.

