#### **D. Description, Risks and Justification of Procedures and Data Collection Tools**

**Risk and Benefits.** The primary benefit of this trial is facilitating knowledge regarding the early identification of risk and intervention among Naval personnel. During the study period, participants may become upset or frustrated with technology associated with the mobile application itself, or during administration of the interviews or questionnaires. Possible breaches of confidentiality may occur, though risks will be minimized as outlined below. The research may also involve unforeseeable risks.

**Safety Monitoring.** *Procedures for Minimizing Risk.* Training. Members of the research team will receive training on risk assessment, crisis management, and regulatory reporting requirements. Clinical team members will receive additional training about clinical monitoring via the Cogito and MyCAP apps, using developed tools (e.g., clinical decision-tree).

*Risk Identification and Clinical Monitoring.* Informed consent materials (which will be stored within the apps and available for participant download) will contain statements explaining mandatory reporting requirements for information regarding intention to harm self or others. During the informed consent process, all participants will provide multiple phone numbers for personal and/or provider contact in case we are unable to reach the participant during a clinical monitoring outreach call. All participants will be monitored during the study period. Specifically, clinical monitoring will occur via responses to the PHQ-9, BSS, C-SSRS, and for the Cogito group, the Cogito Model Scores. Participants may be outreached in two ways. First, if participants meet the clinical threshold on the PHQ-9, BSS and/or the C-SSRS, they will receive an automatic notification via Cogito Companion or MyCAP smartphone applications with crisis resources. Second, clinical team members will contact participant via phone using the following steps.

*Initial Data Assessment.* Clinical team members will have clinical decision-tree handouts for both groups to help guide decision making. Once a clinical team member has determined the need for clinical outreach, the team member will call the participant. The study team will outreach the participant first, and if the participant does not answer, the study team may proceed to contact the personal and/or provider contacts the participant listed during the consent process.

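### The listed C-SSRS triggers are all ideation items, so the automatic crisis-resource message has no concrete criterion for a reported suicide attempt or self-harm

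*Protocol*

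**What the plan says.** Protocol section IV.C, under C-SSRS Screener Monitoring, opens with a general rule: clinical staff review the responses and "conduct outreach based upon recent and/or current suicidal ideation and/or suicidal or self-harm behaviors". The next sentence makes it concrete. It begins "Specifically, we will outreach if the participant positively endorses thinking about how they may kill themselves" and adds two further criteria: "have had thoughts of killing themselves with intention of acting on these thoughts" and "started to work out details of how to kill themselves".

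The automatic messages are tied to thresholds:

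- Cogito arm, section IV.C: "Using the same clinical thresholds described above, the Cogito app will send an automatic notification to the participant", with crisis and care resources.
- Active Control arm, section IV.C: participants whose PHQ-9, BSS or C-SSRS responses "meet the clinical threshold described above, they will receive an outreach call, as well as automatic notification from MyCAP with resources".
- Both arms, section IV.D, Risk Identification and Clinical Monitoring: "if participants meet the clinical threshold on the PHQ-9, BSS and/or the C-SSRS, they will receive an automatic notification".

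Section IV.A says the Screener covers ideation "as well as suicide-related behavior, such as actual attempts and aborted attempts". Table 1 gives its domain as ideation and behaviour and schedules it at baseline, biweekly and at follow-up.

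**The concern.** The general rule names behaviour and the concrete list leaves it out. A clinician reading the paragraph can act on the general rule. An automatic message cannot: it needs defined responses, and for the C-SSRS only the list supplies them. A reported attempt is among the most serious answers the Screener can return, and in a suicide-prevention trial it should not be left to inference whether that answer releases the crisis-resource message.

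Timing adds to this. Section IV.C has each arm's dashboard reviewed once per business day, with none at weekends or on federal holidays. For a survey completed on a Friday evening, the automatic message is the only study response that the protocol describes before the next business day.

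**Working it through.** No arithmetic beyond counting applies, and the plan gives no figure to reproduce. The check sets the passages side by side.

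**Step 1. The rule against its list (Protocol IV.C and IV.A).**

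| C-SSRS response | In the general rule? | In the concrete list? |
|---|---|---|
| Thinking about method | Yes (ideation) | Yes |
| Intent to act | Yes (ideation) | Yes |
| Working out a plan | Yes (ideation) | Yes |
| Actual attempt | Yes (behaviour) | No |
| Aborted attempt | Yes (behaviour) | No |
| Other self-harm | Yes (behaviour) | No |

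Listed criteria: 3, of which 0 are behaviours. Behaviours that section IV.A names as examples: 2, of which 0 are listed.

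**Step 2. What the messages can draw on.** The three threshold statements quoted above express one rule in three places. None adds a C-SSRS criterion. If the reference back is taken to include the general sentence, behaviour is in scope, but that sentence names no qualifying response and puts no period on recency. A programmer would still have no behaviour rule to enter.

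**Step 3. Whether the other instruments fill the gap (Protocol IV.C, PHQ-9 Monitoring and BSS Monitoring).**

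- PHQ-9 item 9: a response of 2 or 3 prompts a call. A response of 1 is weighed with other dashboard and survey data, which can include a C-SSRS behaviour response. The item asks about thoughts, and the weighing at 1 is a staff judgement about a call, not a stated trigger for the message.
- BSS: a response of 2 on any of items 1 to 4 prompts a call. The item wording is not in the documents. Table 1 gives the domain as suicidal ideation, and no behaviour trigger is described.

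Both may catch some or all of these participants. The documents do not show that they catch all.

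**Step 4. Who would be missed.** With the apps set from the listed criteria, the message fails to fire for a participant who reports a recent attempt or self-harm and also (a) endorses none of method, intent or plan, (b) scores below 2 on item 9, and (c) gives no 2 on BSS items 1 to 4. The documents give no basis for estimating how often this happens.

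**The case against.** The strongest reply is that the main safety action is already in place. The general sentence commits staff to outreach for behaviours. Trained staff review both arms each business day, have decision-tree handouts for both groups, and carry out a structured risk assessment on the call. All participants receive crisis-line information at enrolment. The message supplements the call, and the person who would miss it must fail several other triggers at once. Item-level rules may well sit in the handouts or app settings, which are not shown.

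Most of this stands, and it rules out three stronger readings that a reader might infer.

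- *That a reported attempt would bring no staff call.* The general sentence says otherwise.
- *That control participants are worse off, because their call is tied to a threshold.* The control-arm text describes monitoring as similar to the Cogito arm and bases outreach on survey data, which include the C-SSRS. Nothing there withdraws the commitment on behaviours.
- *That three separate safety rules are defective.* They are one rule, restated.

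The reply does not remove the mismatch between the general rule and its list. Nor does it supply a behaviour criterion for the message, which is the only described response outside staff review hours. Unseen handouts may cover the point, but the protocol should not depend on them for it.

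**Conclusion.** The point holds as an inconsistency within a participant-safety rule, with a limited practical consequence: the automatic crisis-resource message may not fire for a reported attempt or self-harm, in either arm, including when staff review is not due until the next business day. Its size in the text is 0 behaviours among 3 listed criteria. Its size in participants is unknown.

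The conclusion assumes that the apps are configured from the listed criteria and that no unseen decision tree or app setting adds behaviours. If either assumption fails, what remains is a wording correction. No sample size, significance level or power figure depends on it. The change is still worth making, because the Screener already collects the responses and the correction costs little.

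**What to change.** In Protocol section IV.C, C-SSRS Screener Monitoring, keep the general sentence and add to the concrete list any recent actual or aborted attempt, or other suicidal or self-harm behaviour endorsed on the C-SSRS. The clinical leads should set the look-back period, for example since the last survey. State that this one list triggers both the outreach call and the automatic message in both arms, and bring the decision-tree handouts into line.

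The cost is protocol and handout wording, possibly a notification setting in each app, and a few more calls and messages. No new data are needed. The SAP is dated 29 May 2023 and does not say whether follow-up has ended; if it has, the change helps only later use of these rules.

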#### **D. Description, Risks and Justification of Procedures and Data Collection Tools**

**Risk and Benefits.** The primary benefit of this trial is facilitating knowledge regarding the early identification of risk and intervention among Naval personnel. During the study period, participants may become upset or frustrated with technology associated with the mobile application itself, or during administration of the interviews or questionnaires. Possible breaches of confidentiality may occur, though risks will be minimized as outlined below. The research may also involve unforeseeable risks.

**Safety Monitoring.** *Procedures for Minimizing Risk.* Training. Members of the research team will receive training on risk assessment, crisis management, and regulatory reporting requirements. Clinical team members will receive additional training about clinical monitoring via the Cogito and MyCAP apps, using developed tools (e.g., clinical decision-tree).

*Risk Identification and Clinical Monitoring.* Informed consent materials (which will be stored within the apps and available for participant download) will contain statements explaining mandatory reporting requirements for information regarding intention to harm self or others. During the informed consent process, all participants will provide multiple phone numbers for personal and/or provider contact in case we are unable to reach the participant during a clinical monitoring outreach call. All participants will be monitored during the study period. Specifically, clinical monitoring will occur via responses to the PHQ-9, BSS, C-SSRS, and for the Cogito group, the Cogito Model Scores. Participants may be outreached in two ways. First, if participants meet the clinical threshold on the PHQ-9, BSS and/or the C-SSRS, they will receive an automatic notification via Cogito Companion or MyCAP smartphone applications with crisis resources. Second, clinical team members will contact participant via phone using the following steps.

*Initial Data Assessment.* Clinical team members will have clinical decision-tree handouts for both groups to help guide decision making. Once a clinical team member has determined the need for clinical outreach, the team member will call the participant. The study team will outreach the participant first, and if the participant does not answer, the study team may proceed to contact the personal and/or provider contacts the participant listed during the consent process.

*Clinical Outreach Calls.* At the beginning of the call, a locator form will be completed to document the physical location and contact information of the participant in case of imminent risk. The participant may be asked for permission to collect contact information for the participants' mental health or health provider, and/or a secondary contact person for additional safety outreach. Next, the team member will let the participant know that information gathered from the app indicated that the participant may be at increased risk and prompted a check on the participant. During the call, the team member will assess the participant's urge to harm themselves or others, and suicidal intent using the UWRAP. Additional information may be gathered including coping strategies, reasons for living, and assessment of physical/mental health symptoms that may be eliciting suicidal ideation, intent, and/or a plan. Referral assistance to treatment providers (DoD/VA) may also be provided. All information gathered during the clinical call, as well as app monitoring data, will be used to determine level of risk and appropriate action steps to be taken. Three risk levels will be used: 1) imminent acute risk; 2) increased acute risk; or 3) no perceived increased acute risk.

*Imminent Acute Risk.* Clinical team members, [name], the PI, or their designee will stay on the telephone with the participant while another team member immediately calls 911, or the appropriate emergency service to initiate an on-site rescue if such action is clinically indicated.

***Increased Acute Risk.*** If a participant appears to be at increased but not imminent risk of suicide, the clinical team member will provide the participant with crisis resources and encourage use, as well as referrals for treatment. Increased clinical monitoring and continued clinical outreach will occur following this contact until the participant is determined to be at No Perceived Increased Acute Risk.

***No Perceived Increased Acute Risk.*** If a participant appears to be at No Perceived Increased Acute Risk with respect to the platform data and suicide risk assessment, the clinical team member may provide crisis resources and referral information, as indicated.

All participants will be informed that they will continue to be monitored via these platforms over the course of their participation in the study. Each clinical outreach, including steps taken during the outreach call, will be documented per study-specific standard operating procedures (SOPs) and reviewed with Drs. [name] and [name].

***Documentation of Risk.*** Notes from the call and responses to the UWRAP will be documented in electronic study “note to file” for the respective participant for each clinical outreach call. Drs. [name] and [name] will be informed of the clinical call and will sign off on each note to file. Each note to file will be saved electronically in the participant’s study folder for reference and documentation during active participation in the study. Note to file information may be shared with participant’s mental health and/or health providers, with the permission of the participant, or with emergency responders in the case of clinical action for those at imminent risk. Data regarding clinical outreach calls will be compiled. After Action Reviews (AARs) will be conducted following the clinical outreach and these events and forms will be reviewed during clinical and administrative team meetings and with the PI.

***Administrative Monitoring and Outreach.*** Clinical team members also will assess the need for administrative outreach. Administrative outreach most generally will be initiated based on a lack of data being collected. Common issues include: participants’ limited internet connectivity; low frequency of text messaging behaviors; changes in app permission (e.g., location permission); and, lack of responses to surveys or incomplete surveys. In most cases, such issues will be noted by Clinical Team Members who will provide this information to the Research Coordinator and/or Assistant, who will make the administrative outreach calls. These administrative calls will be documented in an administrative log maintained by the study team for tracking purposes. Study team contact information will also be provided in both apps, should the participant encounter any administrative issues. The study team will be the primary contact for resolving any administrative or technical issues related to use of the application.

***Clinical & Administrative Consultation Reviews.*** [name] (clinical) and [name] (administrative) will provide ongoing consultation to members of the research team. They will maintain notes regarding these meetings and will review such notes with the PI.

***Reporting.*** Any adverse event will be reported to the local Institutional Review Board by the PI within 5 days and will be reported to the Safety Monitor and MSRC as indicated.

***Data Management Plan.*** Minimizing risks pertaining to data security will be achieved by employing safeguards). Initially, all data collected via Cogito or REDCap will be stored on the secure server and behind the firewall at CU-AMC. Files will be user-restricted and/or password-protected so that only members of the research team can access the data. Data in electronic form created by the study team will be limited data sets and stored in password protected Word documents, Excel spreadsheets and/or ACCESS databases within a restricted access folder behind the firewall at CU-AMC. A master list of participant names and phone number will be kept in a password-protected electronic file, password known only to an authorized member of the research team as designated by the PI. A separate research identification number spreadsheet will be kept and will include the participant’s names and an assigned unique research identification number (UID) in a password-protected electronic file, known only to the authorized research team members. All data in paper format or original documents containing sensitive information will be stored in locked filing cabinets in the Department of Physical Medicine & Rehabilitation, in administrative offices at CU-AMC.

To facilitate data analysis aggregate de-identified datasets may be stored at the Rocky Mountain Regional VA Medical Center. Files will be user-restricted and/or password-protected so that only members of the research team can access the data. All VA data in electronic form will be limited data sets and stored in password protected Word documents, Excel spreadsheets

and/or ACCESS databases within a restricted access folder on the VA shared drive and on the secure server and behind the VA firewall. The secure VA servers are located in a secure room and are backed up nightly.

*Cogito.* Cogito servers and centralized hardware are locked down both physically and electronically. Networking infrastructure is done through a series of access-controlled devices, which restrict access of outside presences and protect inside resources. Datasets are stored on encrypted volumes or under systems with full disk encryption, as appropriate. Data are encrypted and backed-up externally. Data access is granted under least privilege. Cogito is fully equipped with an internal system for project management and documentation of non-PII (personally identifiable information) research materials. This system is fully backed-up and accessible by all employees, both on and off-site. The computing infrastructure has automated monitoring capacities to alert Cogito engineering for downtime, data anomalies, security risks, and directed attacks. End-point data will be validated and confirmed by members of the research team. Cogito has secured Federal Wide Assurance (FWA) for the Protection of Human Subjects. All participants assigned to the Cogito group will be provided a unique research identification "token." Cogito Corporation will provide the research team with a list of unique tokens prior to study recruitment. Authorized members of the research team will distribute the Cogito token at the time of enrollment to participants assigned to this group. The research team will keep a password-protected list of the assigned Cogito token and the participant's unique research identification number (UID). Cogito Corporation will transfer de-identified data via encrypted Word documents and/or Excel spreadsheets to authorized members of the research team via email at CU-AMC.

*REDCap.* The University of Colorado Anschutz Medical Campus (AMC) REDCap platform is a highly secure, nationally-utilized data management system, and it is housed within the highly-secure environment on the AMC. MyCAP is an app developed for use within REDCap. MyCAP allows research study participants to access and respond to surveys on their mobile devices. The app is protected by a 6-digit passcode chosen by the participant, and data are stored in an encrypted database. Participants' survey responses are synchronized with the REDCap database. All participants assigned to the Active Control group will be provided a unique MyCAP research identification number (ID). A member of the study team will obtain a list of unique MyCAP ID prior to study recruitment. Authorized members of the research team will distribute the MyCAP ID at the time of enrollment to participants assigned to this group. The research team will keep a password-protected list of the assigned MyCAP ID and the participant's unique research identification number (UID). Authorized members of the research team will have secure access to MyCAP/REDCap data, and all data will be transferred and stored securely in a user-restricted study folder, saved on the VA server behind the VA firewall (see below).

*Clinical & Administrative Outreach Data.* All clinical and administrative outreach data will be kept using the participant's assigned UID and protected as described above.

*Military Health System Data.* Data management and security for military health information will be stored securely in accordance with the Guide for DoD Researchers on Using MHS Data, as well as protections in accordance with 32 CFR219, DoDI 3216.02 and other applicable Federal laws, regulations, and DoD policies.

